4 STUDY DRUGS

4.1 Description, Supply and Storage of Investigational Drugs

Classification

Zafirlukast is a synthetic, selective peptide leukotriene receptor antagonist (LTRA).

Mechanism of Action

Zafirlukast is a selective and competitive receptor antagonist of leukotriene D4 and E4 (LTD4 and LTE4), components of slow-reacting substance of anaphylaxis (SRSA). Cysteinyl leukotriene production and receptor occupation have been correlated with the pathophysiology of asthma, including airway edema, smooth muscle constriction, and altered cellular activity associated with the inflammatory process, which contribute to the signs and symptoms of asthma. Patients with asthma were found in one study to be 25- 100 times more sensitive to the bronchoconstricting activity of inhaled LTD4 than non-asthmatic subjects.

In vitro studies demonstrated that zafirlukast antagonized the contractile activity of three leukotrienes (LTC4, LTD4 and LTE4) in conducting airway smooth muscle from laboratory animals and humans. Zafirlukast prevented intradermal LTD4-induced increases in cutaneous vascular permeability and inhibited inhaled LTD4-induced influx of eosinophils into animal lungs. Inhalational challenge studies in sensitized sheep showed that zafirlukast suppressed the airway responses to antigen; this included both the early- and late-phase response and the nonspecific hyper-responsiveness.

In humans, zafirlukast inhibited bronchoconstriction caused by several kinds of inhalational challenges. Pretreatment with single oral doses of zafirlukast inhibited the bronchoconstriction caused by sulfur dioxide and cold air in patients with asthma. Pretreatment with single doses of zafirlukast attenuated the early- and late-phase reaction caused by inhalation of various antigens such as grass, cat dander, ragweed, and mixed antigens in patients with asthma. Zafirlukast also attenuated the increase in bronchial hyper-responsiveness to inhaled histamine that followed inhaled allergen challenge.

Storage

Store at controlled room temperature, 20-25°C (68-77°F). See Investigator Brochure. Protect from light and moisture. Dispense in the original airtight container.

Method of Administration

Because food can reduce the bioavailability of zafirlukast, it should be taken at least 1 hour before or 2 hours after meals.

Patient Care Implications:

Patients should be told that a rare side effect of zafirlukast is hepatic dysfunction, and to contact their physician immediately if they experience symptoms of hepatic dysfunction (e.g. right upper quadrant abdominal pain, nausea, fatigue, lethargy, pruritus, jaundice, flu-like symptoms, and anorexia). Liver failure resulting in liver transplantation and death has occurred in patients taking zafirlukast.

4.1.1 Investigational Drug Zafirlukast

Zafirlukast is available in the following doses for oral administration.

20mg PO twice per day

Complete and updated adverse event information is available in the Investigational Drug Brochure and product package insert.

4.2 Drug Accountability

The Investigational Pharmacist will manage drug accountability records.

4.3 Drug Ordering

UCSF will provide the study drug directly to the patient

4.4 Packaging and Labeling of Study Drugs

Drugs will be packaged and labeled per UCSF institutional standards, adhering to applicable local and federal laws.

5 TREATMENT PLAN**5.1 Dose Modifications and Dosing Delays**

Zafirlukast will be administered in 20mg tablets as a single dose. Although zafirlukast is available as a 10mg tablet as well, there will be no dose modification. Should a patient be unable to tolerate the standard dose of 20mg, she will be removed from this study. Zafirlukast should be stopped prior to expander implant exchange

5.2 Monitoring and Toxicity Management

Each patient receiving zafirlukast will be evaluable for safety. The safety parameters include all laboratory tests and hematological abnormalities, physical findings, and spontaneous reports of adverse events reported to the investigator by patients.

6 STUDY PROCEDURES AND ASSESSMENTS

The study-specific assessments are detailed in this section and outlined in [Table 6 Schedule of Study Procedures and Assessments](#). Screening assessments must be performed from day -28 to day 1, prior to the scheduled mastectomy and tissue-expander placement. Treatment or visit delays for public holidays or weather conditions, patient's personal reasons or per PI discretion

that do not compromise safety do not constitute a protocol violation. Treatment delays may not exceed 3 weeks, unless discussed with the study team for patients with documented benefit.

6.1 Screening Assessments

Must be performed from day -28 to day 1, prior to the scheduled mastectomy and tissue-expander placement:

- Medical history
- Physical examination (including height and weight)
- Vital signs (blood pressure, pulse rate, respiratory rate, temperature)
- Con-Med review
- CBC with differential
- Serum biochemical panel including creatinine, fasting glucose, potassium, sodium, chloride, bicarbonate, ALT/AST, total bilirubin
- Blood or urine pregnancy test

6.2 Assessments and procedures during treatment

Once the patient is confirmed to be eligible based on screening assessments, the following study assessments will be performed. See Table 6 for summary. Cohort A participants will begin treatment with zafirlukast on post-operative day one (+/- 5 days) following placement of tissue expander(s) after the participant is determined safe from a surgical recovery standpoint. Cohort A participants will take zafirlukast twice per day until the patient has completed expansion of the tissue expander. Zafirlukast should be stopped prior to expander implant exchange. Patients will be randomized on the day of surgery by a study personnel other than the surgeon. The surgeon and patient will be informed of the assigned cohort immediately post-surgery.

Research Visits (+/- 1 week)

- Physical examination (including height and weight)
- Vital signs (blood pressure, pulse rate, respiratory rate, temperature)
- Con-Med and AE review
- CBC with differential and platelet count
- Serum biochemical panel including creatinine, fasting glucose, potassium, sodium, chloride, bicarbonate
- Liver function tests: alkaline phosphatase, ALT/AST, total bilirubin (only for Cohort A)

Expander-Implant Exchange

- Tissue specimen collection

End of Treatment (14 days (+/- 3 days) of expander-implant exchange)

- Medical history, physical examination (including height and weight), vital signs (blood pressure, pulse rate, respiratory rate, temperature)
- CBC with differential and platelet count
- Serum biochemical panel including creatinine, fasting glucose, potassium, sodium, chloride, bicarbonate
- Liver function tests: alkaline phosphatase, ALT/AST, total bilirubin (only for Cohort A)
- Con-Med and AE review

Follow up

Patients are followed for two years after implant reconstruction. After implant exchange we will see patients every 2 weeks for the first month, every month for the subsequent 4 months, and, every 6 months for the remainder of the two years. For those patients removed from the treatment, they will be followed as per our standard of care which is monthly for the first six months and then every six months for a total of two years.

- Physical examination (including height and weight), vital signs (blood pressure, pulse rate, respiratory rate, temperature)

Table 6. Schedule of Study Procedures and Assessments

Period/ Procedure	Screening ⁹	Treatment period (+/- 1 week)				Expander- implant exchange	End of Treatment	Follow up visits ⁵
Study Day/Visit Day	Days -28 to Day 1	Mastectomy and Tissue- expander placement (week 0)	Day 15-21 (wk 2)	Day 29-35 (wk 5)	Day 71-77 (wk 11)	Day 113-119 (wk 17) ⁸		
Informed Consent	x							
Baseline Conditions ¹	x							
Tissue Specimen Collection						x		
Zafirlukast ⁶		x						
Medical History	x						x	
Vital Signs	x		x	x	x	x	x	x
Physical Exam	x		x	x	x	x	x	x
Con-med and AE review ⁷		x					x	
CBC w/diff ²	x		x	x	x	x	x	
Chemistry ³	x		x	x	x	x	x	
Liver Function Tests ⁴	x			x			x	
Pregnancy Test (HCG)	x							

1. Baseline conditions assessment per DSMC policy.
2. Including CBC with differential and platelet count.
3. Including creatinine, fasting glucose, potassium, sodium, chloride, bicarbonate.
4. Including alkaline phosphatase, ALT/AST, total bilirubin. For Cohort A only on week 5 and EOT. Alkaline phosphatase is not required for screening.
5. Patients are followed for two years after implant reconstruction. After implant exchange we will see patients every 2 weeks for the first month, every month for the subsequent 4 months, and, every 6 months for the remainder of the two years. For those patients are removed from treatment, they will be followed as per our standard of care which is monthly for the first six months and then every six months for a total of two years.
6. 20mg PO twice per day from Day 1 to Treatment Termination for Cohort A only. Treatment may continue until tissue expansion is complete. Zafirlukast should be stopped prior to expander implant exchange.
7. Con-med and AE review begins 28 days prior to treatment and continues 30 days after treatment termination.
8. As needed .
9. Screening procedures must be completed prior to mastectomy and tissue-expander placement.

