8.2 Definition of Adverse Event

An adverse event (also known as an adverse experience) is defined as any untoward medical occurrence associated with the use of a drug in humans, whether or not considered drug related. More specifically, an adverse event can be any unfavorable and unintended sign (e.g., an abnormal laboratory finding), symptom, or disease temporally associated with the use of a drug, without any judgment about causality. An adverse event can arise from any use of the drug (e.g., off-label use, use in combination with another drug) and from any route of administration, formulation, or dose, including an overdose.

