9.1 Analyses Plans

This is an intention to treat analysis. All patients who were randomized will be evaluated.

Data will be summarized using descriptive statistics by study cohorts. For continuous variables, descriptive statistics will include the number of non-missing values, mean, standard deviation, median, minimum and maximum. For categorical variables, descriptive statistics will include counts and percentages per category by study cohorts.

Primary analysis:

The primary objective of the trial is to determine the capsule contracture between the two study cohorts and the primary efficacy outcome in this trial is capsule thickness at the time of expander-implant exchange. Capsule thickness will be determined by averaging thickness from three separate specimens per patient. The capsule thickness will be analyzed by study cohorts, and t-tests and descriptive statistics with mean, standard deviation and 95% confidence intervals will be used for significance. Missing data will not be imputed. An alpha level of 0.05 will be considered significant for the primary endpoint. For exploratory analysis, the primary endpoint of capsule thickness will be presented as mean \pm SEM and evaluated using analysis of variance (ANOVA) with factors including study cohort, radiotherapy and length of drug treatment.

Secondary Analysis:

For secondary objectives of the trial, we will determine the level of fibrosis and presence of collagen from the biopsy specimens. The level of fibrosis and the presence of collagen will be analyzed descriptively as continuous levels and as ordinal levels with mean, standard deviation and 95% confidence intervals. The difference in the level of fibrosis and relative presence of collagen between study cohorts will be compared using t-tests for significance.

Similar statistical methods will also be employed to analyze the capsule tissue that is removed at the time of expander-implant exchange to determine the level and presence of collagen, fibroblasts and myofibroblasts.

Confounding Factors:

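### Scheduled on-study liver tests are done in Cohort A only, so asymptomatic liver-test abnormalities have no concurrent control, although both cohorts already give blood at the same visits

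*Combined protocol and SAP*

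**What the plan says.** Section 6.2 lists, at research visits and again at end of treatment (EOT), "Liver function tests: alkaline phosphatase, ALT/AST, total bilirubin (only for Cohort A". Table 6 note 4 narrows the timing: "For Cohort A only on week 5 and EOT. Alkaline phosphatase is not required for screening".

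Chemistry has no cohort restriction. Section 6.2 gives it as "Serum biochemical panel including creatinine, fasting glucose, potassium, sodium, chloride, bicarbonate", and Table 6 note 3 has the same content: "Including creatinine, fasting glucose, potassium, sodium, chloride, bicarbonate". Table 6 marks CBC and chemistry at week 5 and EOT, the two on-study points at which Cohort A has liver tests.

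At screening (6.1) every patient has ALT/AST and total bilirubin. This is before mastectomy and before randomisation.

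On the risk itself, the patient-care text in section 4.1 calls hepatic dysfunction a rare side effect and adds: "Liver failure resulting in liver transplantation and death has occurred in patients taking zafirlukast". Section 8.2 includes in its adverse-event definition "any unfavorable and unintended sign (e.g., an abnormal laboratory finding", in a sentence that goes on to require a temporal association with use of a drug. Section 9.1 states generally: "Data will be summarized using descriptive statistics by study cohorts". Section 5.2 names only zafirlukast recipients as evaluable for safety.

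**The concern.** The trial is randomised 1:1, so Cohort B shares Cohort A's surgery, anaesthesia, recovery and background medication. It is the natural reference for any liver-test change. The schedule gives up that reference for the hepatic risk in particular, while keeping it for blood counts, creatinine and electrolytes.

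Two things are at stake. First, asymptomatic elevations are looked for in one arm and not in the other, so a table of laboratory liver findings by cohort would differ between arms even if zafirlukast did nothing. Second, if elevations appear in Cohort A, the plan offers no concurrent values to show whether they are post-operative background or a drug signal. The error can go either way: background may be blamed on the drug, or a real signal may be put down to surgery. Control values not collected during the trial cannot be recovered later.

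**Working it through.** The plan states no figure on liver tests, so there is none to reproduce. The only plan number used is 45 patients per cohort (section 3.2).

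**Step 1: who is tested, and when**

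| Test | Screening (6.1, Table 6) | Week 5 and EOT (6.2, Table 6) |
|---|---|---|
| CBC, chemistry | both cohorts | both cohorts |
| ALT/AST, total bilirubin | both cohorts | Cohort A only |
| Alkaline phosphatase | not required | Cohort A only |

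The on-study chemistry panel contains none of the liver analytes, so it does not fill the gap. No section schedules on-study liver tests in Cohort B or explains their absence.

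**Step 2: what the Cohort A baseline can do.** ALT/AST and bilirubin have a pre-treatment value, so within-patient change can be computed. That baseline precedes mastectomy, and week 5 follows it. By Table 6's column order EOT also follows the exchange operation, and section 3.1 puts the last dose on the day before exchange. Change from baseline therefore mixes drug, surgery and other medication. Alkaline phosphatase has no required baseline in either arm.

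**Step 3: size, under an assumption.** Let p be the proportion of patients with a liver-test elevation for non-drug reasons. The documents give no value, so I take 2% to 10%. With no drug effect and all 45 tested:

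- Expected number flagged in Cohort A = 45p.
- Chance of at least one = 1 − (1 − p)^45. With Cohort B untested, this is also the chance that A shows more than B on scheduled tests.
- With both arms tested, the chance that A shows more than B is the sum over all a > b of Bin(a; 45, p) × Bin(b; 45, p).

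| p | 45p | P(A > B), B untested | P(A > B), both tested |
|---|---|---|---|
| 2% | 0.9 | 60% | 34% |
| 5% | 2.25 | 90% | 40% |
| 10% | 4.5 | 99% | 43% |

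With the plan's 10% attrition (45 × 0.9 = 40.5 tested), the expected counts become 0.02 × 40.5 = 0.8 to 0.10 × 40.5 = 4.1.

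**Step 4: what testing both arms would buy.** The approximate 95% half-width for a difference in proportions is 1.96 × √(2p(1 − p)/45).

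- p = 5%: 1.96 × √(0.095/45) = 0.090, or 9 percentage points.
- p = 10%: 1.96 × √(0.18/45) = 0.124, or 12 percentage points.

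The bias goes, but the comparison remains coarse.

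**The case against.** The strongest reply is that liver testing here serves to monitor treated patients, not to compare arms. The objectives in section 2 include no safety comparison, and section 9.1 specifies none for adverse events or laboratory values; its sentence on summaries by cohort is generic. Section 5.2 limits safety evaluability to zafirlukast recipients. Appendix 1, section 3.3, judges Grade 3 or 4 event rates against the brochure or package insert, and section 8.4 requires the investigator to attribute each recorded event. All of this stands. It explains the gap and lowers its importance, but an external rate and an individual judgement do not supply a concurrent reference for asymptomatic changes after surgery.

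Two stronger readings are tempting and should not be drawn.

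- A reader might infer that hepatic events can be found only in Cohort A. The documents do not support this. AE review in section 6.2 has no cohort restriction, and section 8.1 allows closer assessment when clinically indicated. Symptomatic cases and unscheduled tests can reveal events in Cohort B. Only asymptomatic elevations go unsought. Nor does section 8.2 clearly make an abnormal value in an untreated control an adverse event, since its definition is tied to drug use.
- A reader might infer that the trial is likely to produce a falsely significant result against the drug. Six cases against none would give Fisher p = 0.026, but nobody plans that test, and six exceeds even the 4.5 expected at the highest assumed rate. With no drug effect, the chance of nominal p < 0.05 against zafirlukast is below 0.1%, 2.4% and 29% at background rates of 2%, 5% and 10%.

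It is also fair that no section shows surgery still affecting liver tests at week 5. In addition, section 8.4 enters Grade 3 and above in the database while section 8.6 enters all events, so capture of mild elevations as adverse events is unclear even in Cohort A.

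**Conclusion.** The point holds for scheduled, post-randomisation liver tests. Asymptomatic abnormalities are sought in one arm only, any by-cohort summary of them is subject to detection bias, and the Cohort A baseline is informative but cannot by itself separate drug effect from surgery or other medication. On an assumed non-drug rate of 2% to 10%, about 1 to 4 or 5 of 45 Cohort A patients would be flagged with no drug effect and no scheduled counterpart in Cohort B. The asymmetry itself rests on the text and not on that assumption.

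The consequence is confined to descriptive safety. The capsule-thickness endpoint is untouched, and no formal between-arm safety test is affected because none is planned. This is a cheap improvement to the plan, not a threat to its main conclusion.

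**What to change.** 1. Remove the Cohort A restriction from both liver-test entries in section 6.2 and from Table 6 note 4 ("For Cohort A only on week 5 and EOT"). Run the same panel on the Cohort B blood already drawn at the visits where Cohort A is tested.
2. Reconcile section 6.2, which lists liver tests under research visits generally, with Table 6, which marks week 5 and EOT only. The point holds on either reading.
3. In section 9.1, add a descriptive table of liver-test shifts from baseline by cohort. As laboratory data, it does not depend on how section 8.2 defines an adverse event.
4. As a minor addition, include alkaline phosphatase at screening so that its later values have a baseline.

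Cost by Table 6: 2 time points × 45 controls = at most 90 added panels, plus alkaline phosphatase at screening. If section 6.2 governs, Table 6's visits at weeks 2, 5, 11 and 17 (the last as needed) plus EOT give at most 5 × 45 = 225. No extra visit, needle stick or staff is needed. The downside is a small assay cost and some incidental abnormal results in controls to be handled. The comparison will still be imprecise, at about 9 to 12 percentage points either side for rates of 5% to 10%.

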Patients are routinely followed for two years after undergoing implant-based reconstruction. In this study, we will initially see patients periodically for research visits until tissue expansion has been completed. After implant exchange, we will see patients every 2 weeks for the first month, and every month for the subsequent 4 months. We will then see them every 6 months for the remainder of the two years. Those patients who are removed from treatment will be followed as per our standard of care, which is monthly for the first six months and then every six months for two years. Serious adverse events will be collected for 30 days after the end of treatment, or until death, whichever occurs first. Patients removed from the study for unacceptable treatment-related adverse event(s) will be followed until resolution or stabilization of all treatment-related adverse events to Grade 1 or baseline.

Study drugs:

Zafirlukast 20mg PO BID

Safety assessments:

Safety will be assessed by reviewing adverse events (AEs), laboratory evaluations, physical examination, and spontaneous report. Each patient will be assessed periodically for the development of any toxicity. All AEs and serious AEs (SAEs) will be documented and reported. We will also pay particular attention to adverse events of clinical interest specific to zafirlukast.

Unique aspects of this study:

This is the first study to prospectively investigate the potential of zafirlukast to slow or prevent capsular contracture from occurring.

List of Abbreviations

AE	adverse event
ALP	alkaline phosphatase
ALT	alanine aminotransferase
ANC	absolute neutrophil count
AST	aspartate aminotransferase
BUN	blood urea nitrogen
CBC	complete blood cell (count)
CHR	Committee on Human Research (UCSF IRB)
CR	complete response
CRC	Clinical Research Coordinator
CRF	case report form
CSF	cerebral spinal fluid
CT	computerized tomography
CTCEA	Common Terminology Criteria for Adverse Events
CTEP	Cancer Therapy Evaluation Program
CTMS	Clinical Trial Management System
DFS	disease-free survival
DLT	dose limiting toxicity
DSMC	Data and Safety Monitoring Committee
DSMP	Data and Safety Monitoring Plan
FDA	Food and Drug Administration
GCP	Good Clinical Practice
HDFCCC	Helen Diller Family Comprehensive Cancer Center
HGB	Hemoglobin
HIV	human immunodeficiency virus
ICH	International Conference on Harmonization
IND	investigational new drug application
IP	investigational product
IRB	Institutional Review Board

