3 STUDY DESIGN

3.1 Characteristics

We propose a 2-arm, 90 patient (45 per cohort) trial in patients who will be undergoing mastectomy with immediate tissue-expander reconstruction to determine whether treatment with zafirlukast (20mg PO BID) can reduce or prevent the development of capsular contracture. All patients undergoing mastectomy with immediate tissue-expander placement will be approached

in clinic at the time of their initial consultation with the plastic surgeon and enrolled in the trial at this point. Approximately 60 women undergo mastectomy with tissue-expander reconstruction at our institution per year, thus enrollment will occur over a two-year period.

Patients will be block randomized 1:1 into two cohorts: treatment with zafirlukast and the standard of care, or standard of care alone. Patients will begin treatment with zafirlukast on post-operative day one (+/- 5 days) following placement of tissue expander(s) after the participant is determined safe from a surgical recovery standpoint. They will be continued on the standard dosing (20mg PO twice per day) of zafirlukast through expander fill. Last dose of Zafirlukast will be administered the day prior to expander implant exchange procedure. Patients will be seen every 1 to 2 weeks for expander fill, and will be assessed clinically (refer to section 6.2 for research visits). The treating physician will determine the frequency of visits based on each patient's expander need.

During expander-implant exchange, three representative sections of the expander capsule will be collected: medial, lateral and anterior capsule specimens. These specimens will be bisected; half will be sent to pathology and half will be collected by the [name] lab. Gross and microscopic determination of capsule thickness will be performed by the pathology department. The [name] lab will fix and stain the tissues to look for the presence of collagen, level of fibrosis, and number of myofibroblasts. Fibrosis level and collagen presence will be determined by performing immunohistochemistry with a Trichrome stain of the tissues, as well as Western blot analysis with Collagen-1. Myofibroblasts will be detected using immunohistochemistry with commercially available antibodies.

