6.6 Survival Follow-up

6.6.1 Discontinuation of Therapy

The Investigator will withdraw a patient whenever continued participation is no longer in the patient's best interests. Reasons for withdrawing a patient include, but are not limited to, disease progression, the occurrence of an adverse event or a concurrent illness, a patient's request to end participation, or simply significant uncertainty on the part of the Investigator that continued participation is prudent. There may also be administrative reasons to terminate participation, such as concern about a patient's compliance with the prescribed treatment regimen.

When a subject discontinues/withdraws prior to trial completion, all applicable activities scheduled for the final trial visit should be performed at the time of discontinuation. Any adverse events which are present at the time of discontinuation/withdrawal should be followed in accordance with the safety requirements outlined in Section 8.

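### Section 6.2 lists Cohort A liver tests at research visits with no week limit, but Table 6 schedules only one on-drug liver test, at week 5

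*Combined protocol and SAP*

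**What the plan says.** **Text.** Under Research Visits, section 6.2 includes "Liver function tests: alkaline phosphatase, ALT/AST, total bilirubin (only for Cohort A"). The restriction is by cohort, not by week. The same item appears again under End of Treatment.

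**Table.** The liver-test row of Table 6 is marked at screening, week 5 and EOT. Note 4 confirms this: "For Cohort A only on week 5 and EOT". The chemistry panel at the other visits (note 3) is creatinine, glucose and electrolytes. It contains no ALT, AST or bilirubin.

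**How the two relate.** Section 6 opens with "The study-specific assessments are detailed in this section and outlined in" Table 6, and 6.2 refers to the table as a summary. No precedence rule is given.

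**Dosing.** Section 3.1 says "Last dose of Zafirlukast will be administered the day prior to expander implant exchange procedure". Sections 6.2 and 6.4 and note 6 of Table 6 also allow dosing to end when expansion is complete. Section 6.2 places EOT 14 (+/- 3) days from exchange.

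**Liver risk.** Section 4.1: "Patients should be told that a rare side effect of zafirlukast is hepatic dysfunction", and "Liver failure resulting in liver transplantation and death has occurred in patients taking zafirlukast". The synopsis, under safety assessments, adds: "We will also pay particular attention to adverse events of clinical interest specific to zafirlukast".

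**The concern.** Four other items in the 6.2 research-visit list (physical examination, vital signs, CBC and chemistry) are marked in Table 6 at weeks 2, 5, 11 and 17. Liver tests are marked at week 5 alone. Either the table omits tests that the text intends, or the text leaves out a restriction that the table intends. The protocol does not say which.

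Symptomatic liver injury has other routes to detection: patients are told which symptoms to report, and section 8.1 allows more frequent assessment when clinically indicated. A silent rise in ALT or bilirubin depends mainly on scheduled blood tests. Entry allows AST and ALT up to 2.5 x ULN (section 3.3.1), so some patients may start with raised enzymes. Staff who take the table as their checklist would have one scheduled on-drug look at the liver, early in a course that may last about 16 weeks.

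**Working it through.** The plan gives no figure for this, so there is none to reproduce. The check is calendar arithmetic.

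**Inputs**
- Visit days (Table 6): week 2 = Day 15-21, week 5 = Day 29-35, week 11 = Day 71-77, exchange column (week 17) = Day 113-119. Note 8 marks the last as needed.
- First dose: Day 1 (3.1 and 6.2 allow +/- 5 days).
- Last dose: the day before exchange (3.1), so Day 112-118.
- EOT: exchange + 14 (+/- 3) days.
- Cohort A: 45 patients (3.2).

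**Step 1: is EOT on drug?** The interval from last dose to EOT is 1 + 11 = 12 days to 1 + 17 = 18 days, and longer if dosing ends at completed expansion. EOT is off drug, so week 5 is the only on-drug liver test that Table 6 schedules.

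**Step 2: share of treatment after the last scheduled on-drug test.** Share = (last dose day - last test day) / last dose day.

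| Case | Shortest tail | Longest tail |
|---|---|---|
| Table 6, exchange at week 17 | (112 - 35)/112 = 77/112 = 69% | (118 - 29)/118 = 89/118 = 75% |
| Tests also at weeks 2 and 11, exchange at week 17 | (112 - 77)/112 = 35/112 = 31% | (118 - 71)/118 = 47/118 = 40% |
| Table 6, dosing ends near week 11 (Day 71-77) | (71 - 35)/71 = 51% | (77 - 29)/77 = 62% |

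Applying the +/- 1 week window to both the week 5 test and the exchange widens the first row to (105 - 42)/105 = 60% and (125 - 22)/125 = 82%. A later exchange raises the Table 6 share further.

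**Step 3: average wait for a scheduled test.** This is illustrative. It assumes that a silent rise starts on any treatment day with equal chance and then persists. Take mid-window days: tests on Days 18, 32 and 74, exchange on Day 116, last dose on Day 115, EOT on Day 130.
- Table 6 (Day 32, EOT): waits for onset on Days 1-32 sum to 496, and on Days 33-115 to 4,648. 5,144/115 = 44.7 days.
- Weeks 2, 5, 11 and EOT: 153 + 91 + 861 + 1,435 = 2,540. 2,540/115 = 22.1 days.
- With a week-17 test on Day 116 as well: 153 + 91 + 861 + 861 = 1,966. 1,966/115 = 17.1 days.

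**Step 4: panels between screening and EOT.** Table 6: 45 x 1 = 45. Weeks 2, 5 and 11: 45 x 3 = 135, which is 90 more. With week 17: 45 x 4 = 180, which is 135 more. These are upper limits, since not every patient will reach every visit.

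**The case against.** The strongest defence is that 6.2 names the assessments and Table 6 sets their timing. Section 6.2 names no weeks. Weeks 2, 5 and 11 come from the table's columns, and note 4 is the only text that assigns weeks to liver tests. That reading is workable, but section 6 treats the text as the detail and the table as the outline, which points the other way. The ambiguity stands.

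Several stronger readings are tempting but not supported:

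- **That the two texts cannot both be followed.** They can: testing at every research visit includes week 5, and both texts list EOT.
- **That Table 6 permits liver tests only at week 5.** In note 4 the word "only" may attach to Cohort A, as it does in 6.2, and nothing bars extra tests. The table schedules one on-drug test; it does not forbid others.
- **That a patient who stops before week 5 goes untested.** Section 6.6.1 says "all applicable activities scheduled for the final trial visit should be performed at the time of discontinuation", and the natural reading is the EOT assessments, liver tests included.
- **That 70% is a fixed property of the design.** It assumes exchange at week 17, which is as needed.
- **That some number of liver injuries would be missed.** The documents give no rate of silent enzyme rise and call hepatic dysfunction rare.

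Other safeguards also count: expander-fill visits every 1 to 2 weeks with clinical assessment (3.1), adverse event review to 30 days after treatment (note 7), baseline liver limits (3.3.1), and notification of the Data and Safety Monitoring Committee if Grade 3 or 4 events exceed the known rate (Appendix 1, 3.3). They limit the harm, but none of them schedules a liver test.

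Finally, no text sets a required testing frequency, so the preference for more tests rests on low cost and the stated liver risk. That is fair. It is also fair that week 17 carries the other research-visit laboratory tests, so a literal reading of 6.2 may include a liver test there. The fix allows for this.

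**Conclusion.** The mismatch is real and concerns safety monitoring. Section 6.2 lists Cohort A liver tests at research visits without a week limit, Table 6 schedules one on-drug test, and no text says which governs. With exchange at week 17 and the last dose the day before, 69-75% of treatment lies beyond the last scheduled on-drug liver test under Table 6, against 31-40% with weeks 2 and 11 added. If dosing ends near week 11 the Table 6 share is about 51-62%; with a later exchange it is higher. These figures take Day 1 as first dose and, apart from the stated 60-82% range, the nominal visit days. The average waits in step 3 rest further on the assumed uniform onset and persistent rise.

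A reader might infer that this affects the efficacy result. It does not: capsule thickness and its analysis use no liver data. The case for change is a low-cost gain in patient safety and a single schedule for staff to follow.

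**What to change.** In Table 6, mark Cohort A liver function tests at weeks 2 and 11, and in the week-17 column when that visit takes place, because CBC and chemistry are drawn there too. Change note 4 to say that, after screening, liver tests are for Cohort A only, at weeks 2, 5, 11, 17 (when that visit occurs) and EOT. Section 6.2 can then stand as written.

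Cost: two or three table marks and one note. Blood is already taken at these visits, so there are no extra visits or needle sticks. The laboratory load rises by about 90 liver panels (2 x 45), or up to 135 (3 x 45) with week 17. The downside is that some mild, transient enzyme rises will be found and need a repeat test.

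Restricting 6.2 to week 5 would also remove the ambiguity, but it would leave a single scheduled on-drug test and so would not improve monitoring.
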